9.2.2. Sample Size Sensitivity

There was no need to perform sample size sensitivity analysis.

9.2.3. Sample Size Re-estimation or Adjustment

Sample size re-estimation is not planned for this study.

9.3. Data Analysis Considerations

9.3.1. Analysis Populations

All Treated Subjects Population: This will consist of all subjects who received at least one dose of study treatment. Safety and clinical activity data will be evaluated based on this population.

The Pharmacokinetic Population: This will consist of those subjects in All Subjects Population and for whom a PK sample is obtained and analyzed.

The Crossover Population will comprise the subset of subjects in Part 1 and Part 2 who had intra-subject Arm A to Arm B crossover. It will be the primary population when summarizing data in Part 1, Part 2 crossover phase.

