4.1. Overall Design

This is a Phase I/II, open-label, 2 arm study to evaluate the safety and clinical activity of GSK2879552 alone, or in combination with azacitidine in subjects with MDS. Eligible subjects with IPSS-R high or very high risk MDS by World Health Organization (WHO) classification, who have failed an HMA will be enrolled in the study.

This study consists of 2 Arms, i.e., monotherapy with GSK2879552 (Arm A) and combination therapy with GSK2879552 and azacitidine (Arm B). Each Arm has Part 1 for safety evaluation followed by Part 2 to evaluate clinical activity. Both Arms will proceed in parallel and subjects will be randomized in Part 2 to receive either GSK2879552 alone or GSK2879552 in combination with azacitidine. In Arm A, approximately 3-6 subjects will receive during Part 1 the RP2D of GSK2879552 determined in FTIH study (200858), i.e., 2 mg once daily to confirm the RP2D for MDS. In Arm B, traditional 3+3 dose escalation procedure will be followed in Part 1 to determine the RP2D of GSK2879552 in combination with azacitidine. Bayesian Logistic Regression Model (BLRM) prediction on DLT rate may also be provided at dose escalation meetings as the supplementary analysis to 3+3 design (See Section 4.3.2. for more details). Once the RP2D of GSK2879552 for MDS is confirmed in both Arms, Part 2 enrolment will open. Each treatment cycle is 28 days and subjects experiencing disease progression on monotherapy (Arm A) will be allowed to cross over (to Arm B) to be treated with the combination at RP2D.

The statistical design and number of subjects to be enrolled in Part 2 is based on the predictive probability of success if enrollment continues until all planned subjects are recruited [Lee, 2008]. The predictive probability design allows for evaluation of stopping rules after each subject once a minimum number of subjects are evaluable. This study will stop only for futility. Final decisions on stopping enrolment will depend on the totality of the data collected.

Figure 1 Study Schematic

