4.3.4. Dose Escalation Committee

A data review team, consisting (at a minimum) of the investigator(s), GSK medical monitor, clinical pharmacologist, clinical scientist, and statistician, will be responsible for determining whether dose escalation during Part 1 should continue as planned according to the 3+3 design rules together with the predicted DLT rates at all dose levels under a Bayesian logistic regression model (BLRM). Prior to the dose escalation decision, the data review team will review all available data on adverse events including non-DLT toxicities, laboratory assessments and other safety evaluations.

4.4. Part 2

Part 2 of the study will be started once the dose escalation has been completed for both arms (A and B), and a dose has been selected for GSK2879552 monotherapy and combination of azacitidine with GSK2879552. Once deemed eligible, subjects will be randomly assigned at study entry to Arm A or Arm B in accordance with the randomization schedule generated by Clinical Statistics, prior to the start of the study, using validated internal software.

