5.2. Exclusion Criteria

A subject will not be eligible for inclusion in this study if any of the following criteria apply:

DIAGNOSTIC ASSESSMENTS AND OTHER CRITERIA

1. AML according to WHO criteria (i.e. bone marrow blasts >20%)
2. Active hepatitis B or hepatitis C treatment
3. Baseline (pre-dose Day 1) Montreal Cognitive Assessment (MOCA) score of 22 or lower

CONCURRENT CONDITIONS/MEDICAL HISTORY

4. History of or concurrent malignancy of solid tumours, except for below:
Exception: Subjects who have been disease-free for 2 years, or subjects with a history of completely resected non-melanoma skin cancer or successfully treated in situ carcinoma are eligible. Consult GSK Medical Monitor if unsure whether second malignancies meet requirements specified above
5. Prior treatment with temozolomide, dacarbazine or procarbazine
6. Prior treatment with poly ADP ribose polymerase (PARP) inhibitors (e.g., olaparib, ABT-888)
7. Currently receiving other anti-cancer therapy (chemotherapy, radiation therapy, immuno-therapy, biologic therapy, hormonal therapy, surgery, and/or tumour embolization)
8. Received major surgery, radiotherapy, or immunotherapy within 4 weeks of GSK2879552 administration
9. Evidence of severe or uncontrolled systemic diseases (e.g., severe/chronic infection, unstable or uncompensated respiratory, renal, or cardiac disease). Any serious and/or unstable pre-existing medical (aside from malignancy exception above), psychiatric disorder, or other conditions that could interfere with subject's safety, obtaining informed consent or compliance to the study procedures, in the opinion of the Investigator
10. Current active liver or biliary disease (with the exception of Gilbert's syndrome or asymptomatic gallstones or otherwise stable chronic liver disease per investigator's assessment)
11. Patients with any major bleeding current or within the past 4 weeks. (e.g. recent GI hemorrhage or neurosurgery).
12. Administration of an investigational drug within 14 days or 5 half-lives, whichever is shorter, preceding the first dose of study treatment(s) in this study.
13. Cardiac abnormalities as evidenced by any of the following:
 - Clinically significant uncontrolled arrhythmias or uncontrolled hypertension.
 - History or evidence of current \geq Class II congestive heart failure as defined by New York Heart Association (NYHA)
 - History of acute coronary syndromes (including unstable angina and myocardial

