6.4. Blinding

This will be an open-label study

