9.2. Sample Size Considerations

9.2.1. Sample Size Assumptions

Part 1: Dose Escalation

The total number of subjects to be enrolled in the dose escalation phase of Part 1 will depend on the number of subjects needed to characterize individual dose combination cohorts. The sample size is not driven by statistical considerations. However, it is anticipated that approximately 10-12 evaluable subjects will be enrolled.

Part 2: Expansion Cohorts

To determine the maximum sample size for Arm A or Arm B, Bayesian predictive adaptive design will be used for testing hypotheses:

H_0 : CBR \leq 30%

H_A : CBR \geq 50%

When maximum sample size is 28, the design will have a Type I error (α) of 0.099 and 81% power with the probability of termination is 0.90 when the treatment is futile and probability of early termination 0.183 when the treatment is effective (true RR=0.5).

In Part 2, a maximum of 28 subjects will be enrolled in Arm A and Arm B expansion cohort, respectively. If both arms enroll the maximum number of subjects, this will result in 56 subjects total randomized to Arm A and Arm B with 1:1 randomization ratio.

Enrollment into Arm A or Arm B may be halted early based on results from interim analyses incorporating emerging response data. Response data from a minimum of 10 evaluable subjects will be required per arm before it may discontinue enrollment for futility.

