9.4.1. Clinical Activity Analyses

The clinical benefit rate (CBR) is defined as the percentage of subjects with a Complete Remission (CR), marrow complete remission (mCR) or a Partial Remission (PR) or a Hematologic Improvement (HI) or Stable Disease (SD) at any time as per disease-specific criteria ([Appendix 5](#) and [Appendix 6](#)). Subjects with unknown or missing response will be treated as non-responders, i.e. these subjects will be included in the denominator when calculating the percentage. The number and types of responses, as outlined in IWG criteria [[Cheson, 2006](#)], will be listed and summarized separately, as appropriate.

The ORR will be reported at the interim and final analysis for each arm specified in Part 2 as well as all evaluable subjects in Part 1 treated at or above RP2D. Part 1 and Part 2 subjects who received the same dose within the same treatment arm may be combined together in the analysis. The estimates along with 95% exact confidence interval (CI) will be provided.

The CBR and ORR differences between the two cohorts will be provided along with corresponding 95% CI. A chi-square test will be used to test for differences between arms if data warrant.

Duration of response is defined as the subset of subjects who show a response (CR, mCR, PR, or HI), the time from first documented evidence of response until the first documented sign of disease progression or death. Duration of response will be summarized descriptively for each arm, if data warrant, using Kaplan-Meier medians and quartiles. Details on rules for censoring will be provided in the RAP.

For the analysis of **Progression-free survival (PFS)**, if the subject received subsequent anti-cancer therapy prior to the date of documented events, PFS will be censored at the last adequate assessment (e.g. assessment where visit level response is CR, mCR, PR, HI or SD) prior to the initiation of therapy. Progressive disease (PD) will also be defined per standard criteria. Otherwise, if the subject does not have a documented date of events, PFS will be censored at the date of the last adequate assessment. Further details on rules for censoring will be provided in the RAP. PFS will be summarized by arm and dose using Kaplan-Meier quantile estimates along with 2-sided 95% CIs at the time of final analysis, if data warrant.

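### The planned Arm A versus Arm B difference in CBR and ORR is not a clean randomised comparison: it can omit randomised subjects who were never dosed and include non-randomised Part 1 subjects

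*Protocol*

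**What the plan says.** **Design.** Section 4.1 says that "subjects will be randomized in Part 2 to receive either GSK2879552 alone or GSK2879552 in combination with azacitidine". Section 4.4 places the assignment early: "Once deemed eligible, subjects will be randomly assigned at study entry to Arm A or Arm B". Section 9.2.1 gives the size if both arms fill: "56 subjects total randomized to Arm A and Arm B with 1:1 randomization ratio". On blinding, section 6.4 reads: "This will be an open-label study".

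**Population.** Section 9.3.1 defines All Treated Subjects as those with at least one dose of study treatment and continues: "Safety and clinical activity data will be evaluated based on this population". The other populations are Pharmacokinetic and Crossover (9.3.1) and All Evaluable Subjects (9.1.2 and 9.3.2.1), the last used for interim decisions and, if data warrant, summaries of response. None is defined as all randomised subjects.

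**Comparison.** Section 9.4.1 commits to an estimate: "The CBR and ORR differences between the two cohorts will be provided along with corresponding 95% CI". A chi-square test follows if data warrant. Section 9.1.2 sets no formal hypothesis between arms and has CBR and ORR reported for each arm separately.

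**Part 1 subjects.** Section 9.1.2 says that subjects from both parts with the same starting dose will be analysed together. Section 9.4.1 says that those on the same dose within an arm may be combined. Under section 6.3, Part 1 assignment is by investigator discretion and/or slot availability.

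**Missing response.** Section 9.4.1 counts unknown or missing response as non-response and keeps the subject in the denominator.

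**The concern.** A difference between arms, reported with a confidence interval from a randomised part, will be read as a randomised comparison. Two rules in the plan work against that reading.

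First, a subject who is randomised, learns the arm and leaves before the first dose is not in All Treated. The missing-response rule in 9.4.1 cannot bring this subject back, because the population rule acts first. Nor is this subject a screen failure, since section 5.3 reserves that term for subjects never randomised. Because assignment is open, such losses could depend on the arm. The arms differ visibly: one is an oral drug alone, while the other adds azacitidine and, by the Time and Events tables, visits on Days 1-7 of each later cycle, in subjects who have already failed a hypomethylating agent. The direction of any imbalance cannot be told from the protocol, and no rate is given.

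Second, pooling same-dose Part 1 subjects would put into each arm people whose arm was chosen by an investigator or by an open slot.

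At stake is the interpretation of a secondary, descriptive contrast, not a go/no-go decision.

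**Working it through.** **1. The plan's own figures.** An exact binomial recursion over the Table 5 futility looks reproduces the continuation probabilities in every row through 26 subjects (for example 0.8507 and 0.9893 at 10 subjects, 0.2059 and 0.8927 at 26). The chance of never stopping and reaching at least 12 of 28 is 0.0991 at CBR 0.30 and 0.8174 at CBR 0.50, against the stated 0.099 and 81%. The single-arm design is not in dispute.

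**2. Undosed subjects, worst case.** Inputs: 28 randomised per arm (9.2.1), true CBR 30% in both arms (the null value in 9.1.2), and, as an assumption, 3 would-be non-responders leaving one arm before dosing.

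- Expected responders in that arm: 0.30 × 28 = 8.4.
- Treated-only rate: 8.4 / 25 = 33.6%.
- Spurious difference: 33.6 − 30.0 = 3.6 points.

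**3. Precision.** At 30% in both arms, the 95% half-width of the difference is 1.96 × √(2 × 0.30 × 0.70 / 28) = 1.96 × √0.015 = 0.240, or 24 points.

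**4. Loss unrelated to response.** With the same 3 of 28 lost at random, the treated-only rate stays at 30% in expectation. Counting them as non-responders gives 0.30 × 25 / 28 = 26.8%, a shift of −3.2 points.

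**5. An assumed data set.** 28 randomised per arm, 8 responders in Arm A, 14 in Arm B, and k undosed in Arm A (Wald interval; Pearson chi-square without continuity correction):

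| Analysis | Difference (B − A) | 95% CI | p |
|---|---|---|---|
| All randomised, any k | 0.214 | −0.035 to 0.464 | 0.10 |
| Treated only, k = 1 | 0.204 | −0.049 to 0.457 | 0.12 |
| Treated only, k = 3 | 0.180 | −0.080 to 0.440 | 0.18 |
| Treated only, k = 6 | 0.136 | −0.137 to 0.410 | 0.34 |

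With k = 0 the two analyses are identical. Every interval includes zero.

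**6. Part 1 subjects.** Section 4.8 plans 6 + 28 in Arm A and 12 + 28 in Arm B. If all 6 Part 1 subjects in Arm A are at the dose taken forward, they form 6 / 34 = 17.6% of the pooled arm. In Arm B the share is 6 / 34 = 17.6% if 6 of the 12 are at that dose, and 12 / 40 = 30.0% if all 12 are. How many will be at the chosen dose is unknown, and the documents give no basis for the size or direction of any resulting bias.

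**The case against.** **The comparison is descriptive.** Section 9.1.2 disclaims any formal between-arm hypothesis, each arm is judged on its own, and no decision rule uses the difference. All Treated is an ordinary choice in an early-phase activity study. This stands and limits the importance of the point.

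**The effect is small or absent.** The 3.6 points needs every loss in one arm and every lost subject a non-responder, and it is small beside 24 points. In the assumed data set no conclusion changes. This also stands.

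**Counting undosed subjects as failures has its own distortion.** Step 4 shows −3.2 points under random loss. This stands as a reason to show both versions. It does not make the treated-only version the one that respects the randomisation.

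**Part 1 may not enter the difference.** Section 9.4.1 speaks of two cohorts, which could mean the two Part 2 expansion cohorts, and its pooling is optional. But the pooling sentence comes shortly before the difference, and 9.1.2 words pooling as definite, so the text leaves the matter open.

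**Stronger readings that the documents do not support.** A reader might infer that All Treated is the only population for response. It is not: All Evaluable Subjects (9.3.2.1) is a second one, and its wording does not require a dose. It serves the interim decisions and optional summaries, however, and is not named for the 9.4.1 difference. A reader might also see a sure route to post-randomisation exclusion in this criterion of section 5.2: "Baseline (pre-dose Day 1) Montreal Cognitive Assessment (MOCA) score of 22 or lower". But section 4.4 assigns subjects once deemed eligible, MOCA is also done at screening, and the protocol does not say that the Day 1 test follows randomisation.

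**Conclusion.** The point holds as a minor, inexpensive improvement. The plan reports a between-arm difference from a randomised, open-label part on a population defined by dosing, and it permits non-randomised Part 1 subjects into the same analysis. So the difference cannot be taken as a clean randomised comparison.

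Its size rests on assumptions. With no undosed subjects that part of the problem is nil. With 3 of 28 would-be non-responders lost from one arm at a true CBR of 30% it is 3.6 points, against a half-width of about 24. For Part 1, only the possible share of non-randomised subjects can be stated, not a bias.

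One might go further and say that the primary Part 2 result is inflated, since 12 responders are 42.9% of 28 but 50.0% of 24. That does not follow. The primary analysis is a single-arm test, for which a treated population is usual, and its success rule is a count of 12 out of 28. Nor do the documents say that randomisation was introduced to support a formal comparison.

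**What to change.** In 9.4.1, for the between-arm CBR and ORR differences and any chi-square test only:

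- use all subjects randomised in Part 2, in the arm assigned;
- count never-dosed subjects as non-responders, in line with the missing-response rule already there;
- exclude Part 1 subjects.

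Add the matching population to 9.3.1. Keep All Treated for safety, and keep the planned populations for the single-arm tests and futility looks.

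The cost is one definition and one clause. Rates in the comparison may be slightly lower than in the single-arm tables. Unequal loss unrelated to response would slightly lower the rate in the affected arm, so the All Treated difference can be shown alongside, with the number randomised but not dosed in each arm.

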9.3.2. Interim Analysis

No formal interim analysis will be performed. Review of all available safety and pharmacokinetic data will be performed after completion of each dosing cohort.

In Part 1, to further facilitate dose escalation/de-escalation decisions, an adaptive Bayesian logistic regression model (BLRM) may be utilized to predict the probability of DLT at the dose levels yet to be tested.

Prior distribution of the parameter for azacitidine will be calculated based on the toxicity data observed in the first time in human (FTIH) study of GSK2879552 where GSK2879552 is administered alone; similarly, prior distribution of the parameter for Azacitidine will be determined based on data observed in the study where Azacitidine is administered alone; a non-informative prior will be assumed for the other parameters which accounts for the combination of the two compounds. The model will be used only as a guide for what further doses to study in the presence of DLTs. The primary considerations for dose escalation/de-escalation will be based on the rules described in Section 4.3. Further details on the model as well as prior distributions will be included in the Reporting and Analysis Plan (RAP).

9.3.2.1. Part 2 Cohort Expansion

Interim data will be evaluated to monitor efficacy and safety. Enrollment may be stopped early for futility, should various criteria occur based on accrued data. The decision criteria for early stop for futility based on Bayesian Adaptive design are described in Section 9.1.2. The decision will be made for each individual cohort.

The study population used for decision-making at the interim analyses during Part 2 (Expansion Cohort) will be termed All Evaluable Subjects defined in Section 9.1.2. This will be the population for Bayesian adaptive design described in Section 9.1.2 and summaries of response if data warrant. Any evaluable subject from Part 1 of the study who has the same initial dose as in Part 2 will be included in this analysis. Because subjects enroll at different times, not all subjects will have been on the study long enough to have a single or multiple disease assessments. Since disease assessments are to be completed every 4 weeks, subjects who have at least one post-baseline disease assessment or have progressed or died or permanently withdraw from the study will be included in this population.

9.4. Key Elements of Analysis Plan

Data will be listed and summarized according to the GSK reporting standards, where applicable. Data will be listed and summarized mostly by doses. Separate analyses will be provided for Part I and in Part II where applicable. In some instances, analysis may also be generated based on the dose of GSK2879552. Data from Part I and Part II may be combined for some analyses at the end of the trial, for subjects treated at the same dose level. Complete details will be documented in the Reporting and Analysis Plan (RAP). Any deviations from, or additions to, the original analysis plan described in this protocol will be documented in the RAP and final study report.

As it is anticipated that accrual will be spread thinly across centers and summaries of data by center would unlikely be informative, therefore data from all participating centers will be pooled prior to analysis.

All data up to the time of study completion/withdrawal from study will be included in the analysis, regardless of duration of treatment.

As the duration of treatment for a given subject will depend on efficacy and tolerability, the duration of follow-up will vary between subjects. Consequently there will be no imputation for missing data.

Demographic and baseline characteristics will be summarized.

9.4.1. Clinical Activity Analyses

The clinical benefit rate (CBR) is defined as the percentage of subjects with a Complete Remission (CR), marrow complete remission (mCR) or a Partial Remission (PR) or a Hematologic Improvement (HI) or Stable Disease (SD) at any time as per disease-specific criteria ([Appendix 5](#) and [Appendix 6](#)). Subjects with unknown or missing response will be treated as non-responders, i.e. these subjects will be included in the denominator when calculating the percentage. The number and types of responses, as outlined in IWG criteria [[Cheson, 2006](#)], will be listed and summarized separately, as appropriate.

The ORR will be reported at the interim and final analysis for each arm specified in Part 2 as well as all evaluable subjects in Part 1 treated at or above RP2D. Part 1 and Part 2 subjects who received the same dose within the same treatment arm may be combined together in the analysis. The estimates along with 95% exact confidence interval (CI) will be provided.

The CBR and ORR differences between the two cohorts will be provided along with corresponding 95% CI. A chi-square test will be used to test for differences between arms if data warrant.

Duration of response is defined as the subset of subjects who show a response (CR, mCR, PR, or HI), the time from first documented evidence of response until the first documented sign of disease progression or death. Duration of response will be summarized descriptively for each arm, if data warrant, using Kaplan-Meier medians and quartiles. Details on rules for censoring will be provided in the RAP.

For the analysis of **Progression-free survival (PFS)**, if the subject received subsequent anti-cancer therapy prior to the date of documented events, PFS will be censored at the last adequate assessment (e.g. assessment where visit level response is CR, mCR, PR, HI or SD) prior to the initiation of therapy. Progressive disease (PD) will also be defined per standard criteria. Otherwise, if the subject does not have a documented date of events, PFS will be censored at the date of the last adequate assessment. Further details on rules for censoring will be provided in the RAP. PFS will be summarized by arm and dose using Kaplan-Meier quantile estimates along with 2-sided 95% CIs at the time of final analysis, if data warrant.

For the analysis of **overall survival (OS)**, the last date of known contact will be used for those subjects who have not died at the time of analysis; such subjects will be considered censored. Further details on rules for censoring will be provided in the RAP. OS will be

summarized by arm and dose using Kaplan-Meier quantile estimates along with 2-sided 95% CIs at the time of final analysis, if data warrant.

